The Benefit of Mindfulness-Based Intervention Using A Wearable Wellness Brain Sensing Device in the Treatment of Post Covid Symptoms

NCT05199233

07 Nov 2024

Mayo Clinic - NCT05199233

General Study Information

Principal Investigator: [name]

Co-principal investigators: [name] MD

Study Title: The Benefit of Mindfulness-Based Intervention Using A Wearable Wellness Brain Sensing

Device (Muse-STM) in the Treatment of Post Covid Symptoms

As of 07 Nov 2024

Research Ouestion and Aims

Hypothesis:

Post acute sequelae of SARS-CoV-2 infection (PASC), also known as "long haul covid" or Post-COVID Syndrome, is a significant cause of morbidity and disability in patients who have had COVID-19 with an estimated 10-30% of patients developing PASC with symptoms lingering for months and even years. These symptoms occur in a typical pattern, often including fatigue with post-exertional malaise, dyspnea, widespread pain, subjective cognitive dysfunction (often referred to as "brain fog"), and orthostatic intolerance and remain persistent. These can manifest in the post-covid patient as difficulty breathing or shortness of breath, tiredness or fatigue, difficulty thinking or concentrating, cough, chest and/or stomach pain, headache, palpitations, joint and/or muscle pain, parasthesias, diarrhea, increased anxiety and stress, as well as sleep problems.

We postulate that using a novel biofeedback-assisted meditation device (Muse-STM) daily can enhance calm state brain activity and parasympathetic nervous system activity in post-covid patients. We hypothesize that greater amount of time the patient uses this tool will directly correlate with improvements in stress, resilience, and overall quality of life.

Aims, purpose, or objectives:

In this study 60 patients diagnosed with Post-Covid Syndrome (PASC) at Mayo Clinic Rochester will be enrolled in this study.

Primary:

- 1. To study the feasibility of using a wearable brain-sensing wellness device (Muse-STM) to potentially reduce stress and anxiety during Post-Covid, which is characterized with increased stress and anxiety.
- 2. To assess the association between usage of the wearable brain-sensing wellness device (Muse-STM), and quality of life (QOL), subjective stress, anxiety, cognition, through self-assessment surveys.

Exploratory:

1. To collect data at month 6 (3 months post end of treatment) on continued use of Muse-STM past the treatment phase, as a proxy for lifestyle changes.

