All study participants will receive the Muse S^{TM} Headband system at study entry and will be asked to utilize it at least 4 times per week for a minimum of 10 minutes each time over a period of 3 months (12 weeks). They will be followed for a period of 6 months (3 months of treatment and 3 months post treatment) according to the schedule below.

We arable for LC

Pls: [name]; [name], PhD

Mayo Clinic - NCT05199233

	Consent /screen /baseline	Treatment Phase				Follow up Phase
Visit No.	1	2	3	4	5	6
Visit Type	Face to Face	Phone	Phone/ Email	Phone/ Email	Face to Face/ Phone/ Email	Face to Face/ Phone/ Email
Visit Days	0	2	30	60	90	180
Consent/Screening/						
Enrollment						
Informed Consent	X					
Inclusion/Exclusion	X					
Demographic and History	X					
Form	Λ					
Safety Data						
Depression	X		X	X	X	X
Adverse Events ¹			X	X	X	X
Concomitant Medication ²	X		X	X	X	X
Intervention						
Instructions for Muse-S TM & Fitbit [®] Tracker	X					
Muse-S TM use	X		X	X	X	
Fitbit [®] Tracker		X			X	X
Outcome						
CBS Cognitive Tests	X				X	X
Anxiety	X		X	X	X	X
Cognition Function	X		X	X	X	X
Emotional Distress	X		X	X	X	X
Quality of Life	X		X	X	X	X
Resilience	X		X	X	X	X
Self-Efficacy	X		X	X	X	X
Sleep	X		X	X	X	X
Stress Scale	X		X	X	X	X
Satisfaction Survey						X
End of Study Forms						X

^{1 =} For visit 5 & 6 only serious adverse events will be newly collected; 2 = For visit 5 & 6, only newly added concomitant medications will be collected

Study Visit Windows:

Each visit will have a window from the midpoint of the prior visit to the midpoint of the latter visit.

Data Collection:

Mayo Clinic - NCT05199233

Subjects will have the options of completing study surveys/questionnaires online via email link to REDCap prior to study visit. If not completed by the time the study visit takes place, the coordinator can provide the iPad digital version of the survey/questionnaire to the subject for the in-person visits or can interview the patient via phone for the telephone visits. If a subject misses a visit, the study staff will connect with the subject to collect what study data is appropriate through a simple virtual connection (email redcap surveys or telephone interview of surveys). Data Collection in this study will utilize REDCap⁴. All other data collection will be entered directly into a password protected system.

Assessments:

Safety:

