Please note: Patients must have access to an iOS or Android capable device to take part in this study in order to interact with the Muse-STM Headband system.

Treatment phase:

During the first three months of study, participants will be asked to complete the online study intervention using the Muse-STM headband. Participants will be contacted via telephone and online (REDCap) for study visits at day 2, 30 and 60. At day 90, they will be asked to return to the clinic for an in-person visit (telephone and online will be alternatives).

Study Follow-Up Visits:

The study will consist of a 6-month visit post baseline (3-month post end of intervention). Participants will be asked to complete an in-person visit, if possible (telephone and online will be the alternative), which will include a second POCUS exam.

Subject Information

Target accrual: We plan to recruit 80 patients diagnosed with Post-Covid Syndrome at Mayo Clinic with the intent of enrolling 60 to study.

Subject population: A total of 60 patients diagnosed with Post-Covid Syndrome at Mayo Clinic who meet the following study criteria:

Inclusion Criteria:

- 1. 18 years of age or older at time of consent
- 2. Identified with Post-Covid Syndrome (PASC) at Mayo Clinic Rochester:

Wearable for LC

PIs: [name]; [name], PhD

Mayo Clinic - NCT05199233

- 3. Not pregnant by subject self-report at time of consent
- 4. Have the ability to provide informed consent
- 5. Have the ability to complete all aspects of this trial
- 6. Have access to an iPhone, iPad, or Android device
- 7. Have no contraindicating comorbid health condition which would interfere with the proper use of the Muse-STM system, as determined by the clinical investigators

Exclusion Criteria:

- 1. Used an investigational drug within the past 30 days
- 2. Anyone that is not on a stable dose of medication for anxiety, depression or sleep
- 3. Currently (within the past 3 weeks) been practicing mindfulness training on a weekly/regular basis
- 4. Currently (within 3 weeks) has been enrolled in another clinical or research program which intervenes on the patients' QOL, or stress
- 5. An unstable medical or mental health condition as determined by the physician investigator

Data Analysis

Data Analysis Plan:

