Demographic characteristics are described using mean and standard deviations or frequencies and percentages based on the type of variable. For the primary aim of assessing feasibility, descriptive statistics and graphical displays will be presented for data obtained on frequency and duration of use over the 12 weeks of treatment. A linear mixed model with repeated measures for each time point that stress and sleep were taken will be utilized to estimate the association between the number of sessions spent using the Muse-STM with the stress and sleep level outcome. As secondary outcomes, the results of the LASA, resilience, coping, and cognitive testing will be analyzed using similar mixed models. In all cases, results will be summarized using point estimates and corresponding 95% confidence intervals. Given the number of outcomes assessed, all analyses will be considered exploratory.

Endpoints:

Primary Hypothesis:

a) Post Covid patients enrolled in this study will find the Muse-STM Headband system easy to use and will use it per protocol.

Secondary Hypotheses:

- a) Stress score will be lower and sleep score will be improved when compared to the baseline measures for those who use the Muse-STM system as directed.
- b) As the use of the Muse-STM system increases, QOL, resilience and coping will improve.

References

1. Ninifaggi F. Physician engagement: mindfulness as part of the pandemic solution. Elsevier Connect. https://www.elsevier.com/connect/physician-engagement-mindfulness-as-part-of-the-pandemic-solution. Updated 11 May 2020. Accessed 11 June 2020, 2020.

- 2. Mayo Clinic Staff. Stress Management. Healthy Lifestyle Web site.

 https://www.mayoclinic.org/healthy-lifestyle/stress-management/in-depth/stress-relievers/art-20047257. Updated 12 March 2019. Accessed 01 June 2020.

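### Exclusion 2, read literally, shuts out patients who take no anxiety, depression or sleep medication, although nothing in the plan states an intent to study only medicated patients

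*Combined protocol and SAP*

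**What the plan says.** Under Subject Information, Exclusion Criteria, item 2 reads "Anyone that is not on a stable dose of medication for anxiety, depression or sleep". It carries no condition limiting it to patients who take such a drug, does not mention patients who take none, and does not define stability.

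The rest of the document describes the population without reference to medication. The aims state "In this study 60 patients diagnosed with Post-Covid Syndrome (PASC) at Mayo Clinic Rochester will be enrolled in this study". The disease criterion among the inclusion criteria is "Identified with Post-Covid Syndrome (PASC) at Mayo Clinic Rochester", and none of the seven inclusion items concerns medication. Target accrual reads "We plan to recruit 80 patients diagnosed with Post-Covid Syndrome at Mayo Clinic with the intent of enrolling 60 to study".

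Two other places touch the subject. Exclusion 5 covers "An unstable medical or mental health condition as determined by the physician investigator". The visit schedule records concomitant medication at baseline and at days 30, 60, 90 and 180, with a footnote that at visits 5 and 6 "only newly added concomitant medications will be collected". Neither says whether an unmedicated patient may enter.

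**The concern.** A stable-medication criterion normally keeps out people whose treatment is in flux, so that a change in score is not produced by a change in drug. That needs a conditional: if the patient takes such a drug, the dose must be settled. The condition is missing here, and without it the sentence removes a second and quite different group, those who take nothing.

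What is at stake is who the feasibility result describes. The primary outcome is adherence to the headband. If the criterion is followed to the letter, adherence is observed only in patients on stable anxiety, depression or sleep medication, and a report written in the language of the aims would present it as adherence in post-COVID syndrome generally. If staff apply the likely intent instead, the enrolled group is broader, but the protocol does not document the rule that was used. A reader cannot tell from the text which of the two groups was studied.

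**Working it through.** The plan states no figure on this point, so there is none to reproduce. The check is a reading of the rule followed by simple arithmetic.

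**Step 1: the rule as written.** Excluded = NOT (on a stable dose of an anxiety, depression or sleep drug).

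| Patient | On a stable dose? | As written | If limited to patients taking such a drug |
|---|---|---|---|
| (a) takes none | no | excluded | eligible |
| (b) takes one, dose changing | no | excluded | excluded |
| (c) takes one, dose stable | yes | eligible | eligible |

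The two readings differ only in row (a). The right-hand column needs a qualifier that the sentence lacks.

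**Step 2: does any other text supply the qualifier?** The aims, the recruitment and consent sections, the seven inclusion criteria, the other four exclusions, the visit schedule and the Data Analysis section do not. Exclusion 5 concerns unstable conditions and is silent on row (a). The schedule records medication without making its use a condition of entry.

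**Step 3: does any text support a medicated-only population?** No. The aims, the target accrual statement and the disease criterion all refer to patients with post-COVID syndrome, without a medication requirement or a reason for one.

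**Step 4: illustration of the recruitment consequence.** Inputs from Target accrual: 80 recruited, 60 enrolled, so 60/80 = 75%. Let s be the share of recruits on a stable dose. The documents do not give s, so every value below is an assumption. If no other criterion removes anyone, the literal rule leaves 80 × s eligible out of 80, and 60/s recruits are needed to enrol 60.

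| Assumed s | Eligible of 80 | Recruits needed for 60 |
|---|---|---|
| 30% | 24 | 60/0.30 = 200 |
| 50% | 40 | 60/0.50 = 120 |
| 60% | 48 | 60/0.60 = 100 |
| 75% | 60 | 60/0.75 = 80 |

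Under the literal rule the 80-to-60 plan therefore requires s of at least 75%. Under the conditional reading, row (a) patients cost nothing in recruitment.

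**The case against.** The strongest reply is that experienced staff will read the criterion in its customary sense, that any such drug must be at a settled dose, and will not turn away an unmedicated patient. The study recruits at one site and promises standardised screening procedures, which lowers the risk of uneven application. All this is fair. Nothing in the documents shows that an unmedicated patient was or would be rejected. But these points concern how the rule may be applied. They do not put the missing condition into the text.

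Four stronger readings are tempting, and the documents do not support them.

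- *The criterion contradicts the primary hypothesis.* It does not. The hypothesis is "Post Covid patients enrolled in this study will find the Muse-STM Headband system easy to use and will use it per protocol", which is limited to those enrolled, and the subject population is likewise defined by the study criteria. What remains is a question of whom the result describes.
- *The rule admits patients whose scores are confounded by drugs and excludes those whose scores are not.* A constant dose does not by itself produce change from baseline, so patients in row (c) are not confounded merely by being medicated.
- *The absence of a look-back lets in patients whose drug changed days ago.* Exclusions 1, 3 and 4 do have windows (30 days, 3 weeks, 3 weeks) and exclusion 2 has none. But a dose changed days ago is not stable in the ordinary sense, and exclusion 5 is a partial backstop. This is missing detail, worth settling in the same edit, and not a separate error.
- *Recruitment will fall short.* The medicated share is unknown. The plan also does not say why 80 become 60, and since consent comes before screening, refusals may account for part of the difference.

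**Conclusion.** The point holds as a defect of wording. Followed literally, exclusion 2 rejects patients with post-COVID syndrome who take no anxiety, depression or sleep medication. This is at odds with the population in the aims and inclusion criteria, and no reason for it is given. It is not evidence that anyone was wrongly excluded, and the likely intent is narrower than the text.

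The consequence is for eligibility and for the population to which the adherence result applies. The analysis methods are unaffected: the primary outcome is descriptive and the plan states "Given the number of outcomes assessed, all analyses will be considered exploratory". The 100 to 200 recruits is an illustration resting on an assumed 60% to 30% stably medicated share with no other losses; it is not an estimate. A clarification should be made, but the defect does not undermine the design.

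**What to change.** Make the exclusion conditional on change. For example: *Any start, stop or dose change of a drug for anxiety, depression or sleep within [period set by the sponsor] before consent.* Then add: *Patients who take no such drug and have had no such change in that period are eligible.* The investigators should first confirm that this is what they mean; if a medicated-only population is intended, the aims and inclusion criteria should say so and give the reason.

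Two details matter. The wording should not be confined to drugs currently taken, because a recently stopped drug is no longer being taken. And the eligibility sentence must refer to the absence of recent change as well as to taking none, or it would let in patients who stopped shortly before consent.

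The documents do not say whether enrolment is complete. If it is, record how the criterion was applied at screening and report the number of participants on such medication at baseline, using the baseline concomitant medication record.

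The cost is a short protocol amendment. A fixed period may exclude or delay a few patients with recent changes.

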Use of Muse-STM Headband systems will be demonstrated to each participant prior to their first mindfulness practice session, which will be completed during the baseline visit with the study coordinator. The study coordinator will present the participant with detailed instructions on how to begin each session. The frequency of the sessions thereafter will be at the participant's discretion according to the study's requirements (daily practice). Mindfulness training will follow the protocol in the Muse-STM

APP, which follows a standard breathing exercise with EEG brain state feedback through the mobile device, as designed by a panel of experienced mindfulness practitioners. In short, the Muse- S^{TM} functions like a $FitBit^{\textcircled{R}}$ like device for the brain.

The study participants can access 3 different types of meditation while using the Muse-STM Headband system. They are as follows:

Wearable for LC PIs: [name]; [name], PhD Mayo Clinic - NCT05199233

• Mind Meditation uses the Muse-STM headband to track the user's brain activity during meditation and translates the brain's activity into guiding sounds. This is a classic focused attention on the breath meditation, where you get real time feedback on your brain. Users get real time feedback to know when they are in focused attention and when their mind is wandering and are cued to return to a state of focused attention (meditation state). Users also see data from their brain after the meditation. Real time feedback during Mind Meditation is the Muse-STM signature meditation and teaches the fundamentals of a meditation practice in remaining in a calm focused attention state and being able to move your mind away from distracting thoughts. This teaches them the skill to notice their minds and learn to direct themselves out of their discursive mind and onto a neutral object like their breath, while giving them neurofeedback to guide them when they are "doing it right" and reinforce the learning. It is recommended that Muse Mind be done daily for a minimum of 5 minutes per day. Users can do more if they choose.

- **Guided Meditation** These are different breathing exercises where different breathing techniques, such as box breathing, 6-4 breathing, etc., are taught to help the individual regulate their breath. The participant is given real time feedback to keep them breathing along in time with the guide.

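### The usage-outcome models do not separate a participant's usual use from change in that use, so self-selection can create, mask or reverse an apparent dose response

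*Combined protocol and SAP*

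**What the plan says.** The Data Analysis Plan specifies "A linear mixed model with repeated measures for each time point that stress and sleep were taken", used to "estimate the association between the number of sessions spent using the Muse-STM with the stress and sleep level outcome". LASA, resilience, coping and cognitive testing "will be analyzed using similar mixed models". No equation is given. The plan does not say whether sessions are counted per interval, cumulatively or as one total per person, and it names no random effects, visit term, baseline score or covariates. Results are point estimates with 95% CIs. All analyses are called exploratory, and the reason given is the number of outcomes.

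Use is not assigned. The Intervention section says: "The frequency of the sessions thereafter will be at the participant's discretion". The Methods section says "All study participants will receive the Muse S" headband at entry, with a request for at least 4 sessions a week for 12 weeks, so there is no comparison group.

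The hypotheses are worded as dose response. The opening Hypothesis expects that "greater amount of time the patient uses this tool will directly correlate with improvements in stress", and secondary hypothesis (b) reads "As the use of the Muse-STM system increases, QOL, resilience and coping will improve".

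Two facts decide what can be done. The Server Data paragraph makes the time and duration of every session available. The visit schedule has stress, sleep, quality of life and resilience at days 0, 30, 60, 90 and 180, but the CBS tests only at days 0, 90 and 180.

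**The concern.** Repeated session counts carry two kinds of information. One is whether habitual heavy users score differently from light users. The other is whether a given person scores better after a period of heavier use. The first is exposed to every stable difference between people, such as severity of illness, motivation and speed of natural recovery. The second is free of those stable differences, though not of everything else.

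A single slope on interval counts is a precision-weighted mix of the two. A slope on one total per person contains only the first. Under either coding, a reader who sets the slope against hypothesis (b) cannot tell whether using the device more goes with feeling better, or whether people who were going to do better used it more. If the more stressed people use it more, a real benefit could be hidden or appear as harm.

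**Working it through.** The documents give no SD, effect size or power for these models, so there is no stated figure to reproduce. The check uses assumed inputs and shows how the answer moves with them.

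**Inputs from the documents.** n = 60; on-treatment scores at days 30, 60 and 90 (T = 3); PSS range 0 to 40; requested use 4 per week, or 4 × 30/7 ≈ 17 sessions per 30 days.

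**Assumptions.** PSS SD 7 and ICC 0.6, so between-person variance is 0.6 × 49 = 29.4 and residual variance is 19.6. Sessions per 30 days have between-person SD 6 and within-person SD 4. Usual use correlates rho with a person's stable stress level. The true within-person effect is 0 unless stated.

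**Step 1: how a single slope blends.** In a random-intercept model, the weights per participant are approximately:
- within: (T - 1) × 4² / 19.6 = 32/19.6 = 1.63
- between: T × (6² + 4²/3) / (19.6 + 3 × 29.4) = 124/107.8 = 1.15

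The between-person share is 1.15/(1.63 + 1.15) = 0.41. At rho = -0.3 the between-person slope is -0.3 × √29.4 × 6 / 41.33 = -0.236 PSS points per session. The single slope is then 0.41 × (-0.236) ≈ -0.097, although the within-person effect is zero. Simulation (1,000 trials per scenario, visit term included) gave -0.236 and -0.097.

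**Step 2: range over the assumptions (ICC 0.4 to 0.8, no baseline covariate).**

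| rho | Single slope per session | 95% CI excludes 0 |
|---|---|---|
| 0 | about 0 | about 5% |
| -0.3 | -0.07 to -0.11 | 18-29% |
| -0.5 | -0.12 to -0.20 | 45-70% |

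At rho = -0.5 and ICC 0.6 the slope is -0.179, and -0.179 × 17 ≈ -3 PSS points per month of requested use, all of it selection. With one session total per person, the CI excludes zero in 48-97% of trials over rho -0.3 to -0.5.

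**Step 3: visit and baseline score added.** Baseline adjustment does not remove the problem if usual use tracks recovery. With a use-recovery correlation of 0.4, the single slope is about -0.25 per 4 sessions and its CI excludes zero in 15% of trials. Adding rho = -0.3 makes this about -0.49 and 39%. The SD of recovery slopes matters: over 0.7 to 1.5 PSS points per visit, the two percentages run 12-24% and 29-43%. The within-person term stays near 0, at 4-6%.

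**Step 4: opposite selection.** With rho = +0.5 and a true within-person effect of -0.10 per session, the single slope is +0.08, the wrong sign. The within-person term gives -0.11.

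**Step 5: what the split does not cure.**
- *Time.* With cumulative sessions, a natural fall of 1 PSS point per visit and no visit term, the within-person CI excludes zero in 95% of trials with no true effect. In the single-slope model, a visit term brings the same error down from 95% to 4%.
- *Reverse causation.* Suppose a bad month lowers that month's use (r = -0.3). The within-person slope is then about -0.3 × √19.6 / 4 = -0.33 per session, or -1.33 per 4 sessions. Simulation gave -1.36, with the CI excluding zero in 91-92% of trials. The single slope did less badly here (-0.72 to -0.74; 75-76%).

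**Step 6: cost in precision.** Standard errors per 4 sessions are 0.43 (within) and 0.29 (single), a ratio of 1.5. For an immediate effect of 0.5 PSS points per 4 sessions, 0.5/0.43 = 1.16 gives power of about 21% and 0.5/0.29 = 1.72 gives about 41%. Simulation gave 22% and 49%.

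**The case against.** The plan claims only an association, calls everything exploratory, and has adherence as its primary outcome, described without a model. That limits the harm and stands. But the exploratory label rests on the number of outcomes, not on self-chosen use, and it does not say which association is being estimated.

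A reader might infer that the plan commits itself to one coefficient that mixes the two effects. It does not: no equation is given, and the single slope is read from the word association in the singular. If sessions are a person total, nothing is mixed, but the slope is then wholly between-person.

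A reader might also infer that hypothesis (b) is a within-person claim and should rest on that coefficient alone. The documents do not say so. The opening Hypothesis can fairly be read as heavier users improving more. Step 5 shows that the within-person term can mislead more than a pooled slope when symptoms drive use. It can also miss a benefit that builds up: for a lasting, accumulating effect of 0.5 PSS points per 4 sessions (assumed), it averaged -0.26 and detected the effect in 10% of trials. These points stand, and they are why both terms should be reported.

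Finally, the split cannot serve every outcome. CBS has one on-treatment score, so interval deviations have nothing to pair with.

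**Conclusion.** The point holds as a cheap improvement. As written, the usage-outcome analyses cannot distinguish who uses the device from what happens when a person uses it more, although the stated hypotheses invite a dose-response reading.

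Under the assumed correlations, with no true effect and with visit and baseline in the model, a single slope's CI excludes zero in roughly 12-43% of trials instead of 5%. With selection the other way, a true benefit can change sign. Size and direction depend on the assumed SDs, ICC and correlations, none of which the documents give. What does not depend on them is that the slope is exposed to selection whenever usual use is related to a person's level or recovery.

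A reader might conclude that any dose response found here would be nothing but self-selection. The documents do not support that: they give no evidence on the strength or sign of selection. The primary feasibility outcome is unaffected.

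**What to change.** For outcomes scored at days 30, 60 and 90 (stress, sleep, LASA, resilience), state in the Data Analysis Plan that:
- sessions are counted over the interval before each score;
- the model includes a visit term and the baseline score;
- use enters as two terms, the participant's mean over the treatment intervals and each interval's deviation from that mean;
- both coefficients are reported with 95% CIs, and neither the between-person term nor any pooled slope is read alone as evidence for hypothesis (b).

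Add two cautions to the text. The between-person term is open to self-selection. The within-person term removes only stable differences between people and can still reflect reverse causation, such as feeling worse and then using the device less. Label the CBS usage association between-person only, because day 90 is its one on-treatment score.

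The cost is a few sentences and no new data, since sessions are already logged. The downside is lower power for the within-person term: 22% against about 40-49% for an assumed immediate effect of 0.5 PSS points per 4 sessions.
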